6.3 Measures to Minimize Bias: Randomization and Blinding

6.3.1 Intervention Assignment

Intervention allocation/randomization will occur centrally using an interactive response technology (IRT) system. At **Visit 3/Day 1/Randomization**, there will be 2 study intervention arms. Participants will be assigned randomly in a 2:1 ratio to ertugliflozin 5 mg or placebo.

At **Visit 5/Week 12**, all eligible participants (Section 6.1) will undergo a second randomization. Eligible participants in the ertugliflozin 5 mg group will be randomized in a 1:1 ratio to either stay on ertugliflozin 5 mg or up-titrate to ertugliflozin 15 mg (Section 8.1.14). Eligible participants in the placebo group will participate in the second randomization, but all will remain on placebo and be mock-titrated to preserve blinding.

If the PK IA (Section 9.7) results in a decision to drop the 15 mg dose, then:

- 1. The second randomization at **Visit 5/Week 12** will be discontinued and the corresponding FS A1C and FFSG should not be performed (the central laboratory A1C will still be performed).
- 2. Ongoing participants who have reached **Visit 5/Week 12** or beyond on study medication will return to the site to have blinded study medication redispensed through IRT to maintain blinding. Participants receiving placebo or ertugliflozin 5 mg will continue to receive the same medication. Participants who are receiving ertugliflozin 15 mg will be down-titrated to the ertugliflozin 5 mg dose for the remainder of the study.

If the ertugliflozin 15 mg dose is continued, the second randomization at **Visit 5/Week 12** will be monitored by the unblinded DMC statistician so that ~30 participants are up-titrated to ertugliflozin 15 mg/day.

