8.1.14 Second Randomization

At **Visit 5/Week 12**, all participants will have an FS A1C measured at the site (Section 8.3.8.1). Participants will undergo a second randomization as outlined in the SoA *if* their FS A1C is \geq 7.0% (53 mmol/mol). At this second randomization, eligible participants on ertugliflozin 5 mg will be assigned to continue on the 5 mg dose or up-titrate to the ertugliflozin 15 mg dose in a 1:1 ratio. Eligible participants in the placebo group will participate in the second randomization, but all will remain on placebo and be mock-titrated to preserve blinding. Note: The up-titration criteria for participants on insulin will include a FFSG \geq 110 mg/dL (6.1 mmol/L) in addition to A1C \geq 7.0% (53 mmol/mol) at **Visit 5/Week 12**. Participants who do not meet the threshold(s) for a second randomization will continue on ertugliflozin 5 mg/placebo. If a participant discontinues study medication before **Visit 5/Week 12**, the second randomization (and related assessments) should not be performed.

At **Visit 5/Week 12**, a second allocation number will be randomly assigned by the IRT system for participants on ertugliflozin 5 mg who meet up-titration criteria. During the study, only the unblinded statistician will have access to this allocation number and its associated treatment assignment. Participants who undergo the second randomization will retain their initial randomization number assigned at **Visit 3/Day 1/Randomization** to uniquely identify them by blinded personnel during the study.

The unblinded statistician who supports the DMC described in Section 9.7 will review the number of participants randomized to the ertugliflozin 5 mg and ertugliflozin 15 mg group at the **Visit 5/Week 12** second randomization and throughout the study. Based on the distribution of participants within the ertugliflozin 5 mg and 15 mg arms, the randomization ratio for the second randomization at **Visit 5/Week 12** may be adjusted in order to achieve approximately 30 participants in the ertugliflozin 15 mg arm.

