9 STATISTICAL ANALYSIS PLAN

This section outlines the statistical analysis strategy and procedures for the study. If, after the study has begun, but prior to any unblinding, changes are made to primary and/or key secondary hypotheses, or the statistical methods related to those hypotheses, then the protocol will be amended (consistent with ICH Guideline E-9). Changes to exploratory or other non-confirmatory analyses made after the protocol has been finalized, but prior to unblinding, will be documented in a supplemental SAP (sSAP) and referenced in the Clinical Study Report (CSR) for the study. Post hoc exploratory analyses will be clearly identified in the CSR.

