Statistical Methods for Key Efficacy/Immunogenicity/ Pharmacokinetic Analyses	The primary hypothesis will be evaluated by comparing ertugliflozin (combined 5 mg and 15 mg doses) to placebo with respect to A1C change from baseline at Week 24. The treatment policy (TP) estimand is expected to be considered primary in some regions. In all other regions, the Treatment Effect (TE) estimand will be primary. The TP estimand will estimate the difference in change from baseline means comparing the effect of being randomized to ertugliflozin versus placebo whereas the TE estimand will estimate the effect of being treated with ertugliflozin versus placebo. The primary analysis approach for the TP estimand will evaluate the treatment difference via a Bayesian borrowing approach using an informative prior distribution derived from a completed adult study of ertugliflozin (MK-8835 P007) and with missing Week 24 A1C data imputed using a Retrieved Dropout (RD) or Washout Imputation (WI) approach. The weight given to the adult prior distribution for the primary hypothesis test will be 0.134. The primary analysis approach for the TE estimand will evaluate the treatment difference via a frequentist analysis using a constrained longitudinal analysis model (cLDA). The key secondary hypotheses will be assessed using an ANCOVA model after imputing missing data using RD or WI. These hypotheses will be tested under only the TP estimand and will apply weights to the treatments as follows: • Participants on ertugliflozin 5 mg who were not re-randomized at Visit 5/Week 12 have a weight of 1 For the hypothesis comparing the addition of ertugliflozin, with dosing optimized according to A1C response, to the addition of placebo, the weights for the re-randomized participants will be defined as follows: • Participants who were re-randomized to 15 mg at Visit 5/Week 12 have a weight of 2		

C Confidential

	 Participants who were re-randomized to 5 mg at Visit 5/Week 12 have a weight of 0. For the hypothesis comparing ertugliflozin 5 mg with placebo the weights for the re-randomized participants will be defined as follows: Participants who were re-randomized to 5 mg at Visit 5/Week 12 have a weight of 2. Participants who were re-randomized to 15 mg at Visit 5/Week 12 have a weight of 0. 	

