9.6 Statistical Methods

Statistical testing and inference for safety analyses are described in Section 9.6.2. Efficacy results that will be deemed to be statistically significant after consideration of the Type I error control strategy are described in Section 9.8. Nominal p-values (ie, unadjusted for multiplicity) may be computed for other efficacy analyses for descriptive purposes rather than for assessing statistical significance.

The primary approach for all efficacy and safety analyses will pool participants from both ertugliflozin dose groups (5 mg and 15 mg) for comparison with placebo. In addition, A1C change from Baseline at Week 24 will be compared for 2 treatment strategies, (1) dose-optimized ertugliflozin versus placebo and (2) ertugliflozin 5 mg versus placebo. Dose-optimized ertugliflozin consists of participants who were randomized to ertugliflozin and either did not meet the re-randomization criterion at Week 12 or who met the re-randomization criterion and were re-randomized to ertugliflozin 15 mg. Descriptive statistics will be used for efficacy and safety endpoints to summarize ertugliflozin data by dose group and by combined doses. Descriptive statistics will also be used to summarize the individual ertugliflozin dose arms in the subset of participants who were re-randomized at Visit 5/Week 12.

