For H3 - The effect of being randomized to ertugliflozin 5 mg versus placebo.

Specific weighting schemes will be used to test H2 and H3. The weighting schemes are defined as follows:

- All participants on placebo have a weight of 1
- All participants on ertugliflozin who were not re-randomized at Visit 5/Week 12 have a weight of 1
- For H2 the hypothesis comparing dose-optimized ertugliflozin to placebo (weighting scheme A):
 - All participants on ertugliflozin who were re-randomized to 5 mg at Visit 5/Week 12 have a weight of 0
 - All participants on ertugliflozin who were re-randomized to 15 mg at Visit 5/Week 12 have a weight of 2
- For H3 the hypothesis comparing ertugliflozin 5 mg with placebo (weighting scheme B):
 - o Participants who were re-randomized to 5 mg at Visit 5/Week 12 have a weight of 2
 - Participants who were re-randomized to 15 mg at Visit 5/Week 12 have a weight of 0

For the key secondary endpoints, treatment group comparisons for the A1C mean change from baseline at Week 24 will be done using an ANCOVA model with treatment, the age and insulin use strata as fixed effects, and baseline measurement as a covariate. Hypotheses H2 and H3 analyses for RD and WI are shown below.

The RD imputation and analysis steps are as follows for H2 and H3 using Rubin's rule for 100 total imputed datasets:

- 1. Within each imputation sample, do the following:
 - a. Impute missing Week 24 values using a normal distribution where the expected change from baseline value is set to the estimated mean change from baseline value from the RD participants in the same treatment group. The standard deviation will be the RMSE derived from the ANCOVA model described above and estimated based on all participants with Week 24 data.
 - b. After step a, each of the 100 resulting datasets will contain the original non-missing data and the imputed data for those with missing Week 24 values.
- 2. The 100 datasets will be analyzed using a weighted ANCOVA model with Baseline A1C and the two stratification factors as covariates. The weights will be defined as listed above and included in the model using the weight option from SAS PROC MIXED. The 100 weighted ANCOVA-based estimates of the treatment difference will be combined using PROC MIANALYZE based on Rubin's rule, which accounts for between and within imputation variability.

The WI imputation and analysis steps are as follows for H2 and H3:

For participants in the ertugliflozin group:

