9.9 Sample Size and Power Calculations

This study will randomize approximately 165 participants using a 2:1 randomization ratio at Visit 3/Day 1/Randomization for ertugliflozin and placebo resulting in approximately 110 participants in the ertugliflozin group (combined doses) and 55 participants in the placebo group.

TP Estimand Power

The type 1 error and power (percent of 95% posterior credible intervals <0) were simulated (10,000 simulations) using the rjags and coda packages in R and the credible intervals were

computed using the HDInterval package. With an informative prior, the type 1 error will exceed 0.05. Using the adult data from 8835-007 and a weight parameter of 0.134, a sample size of 165 will provide approximately 80% power to detect a true difference of -0.6% in the mean change from baseline in A1C between ertugliflozin and placebo, given the SD=1.5% and discontinuations from study medication as of the primary timepoint are approximately 3.9%. The type 1 error and power were estimated based on the WI approach instead of the RD approach given all randomized participants have either completed on or off study medication or have discontinued from the study in Phase A.

Regarding the secondary hypotheses, the assumptions for the efficacy of the dose-optimized ertugliflozin regimen and of the 5 mg ertugliflozin dose are the same as for the pooled ertugliflozin doses. However, the power for the secondary hypotheses will be lower than that of the primary hypothesis on account of the weighting scheme. Based on simulations, the percent reduction in power is 13% of the primary hypothesis power. Thus, the estimated power for each secondary hypothesis is 70%.

TE Estimand Power

Assuming 86% of the participants will have data at Week 24 (14% with missing data due to discontinuation from study medication or censoring after initiation of rescue), 95 participants in the combined ertugliflozin arm and 47 in the placebo arm will provide at least 80% power for the primary hypothesis test assuming that the between-group difference in A1C change from baseline at Week 24 is -0.75% and using a SD of 1.5%. Assumptions of cumulative attrition rates and covariance matrix at Week 6, Week 12 and Week 24 are listed below:

- 1. The cumulative attrition rates (due to dropout and/or censoring due to discontinuation of study medication or initiation of rescue) at Week 6, Week 12, and Week 24 are 4%, 8% and 14%.
- 2. The conditional covariance matrix is

1.11	0.8	0.6

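### The H2 and H3 weights of 2 and 0 assume a 1:1 second randomization, but the protocol lets that ratio change and the SAP does not adapt the weights

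*Combined protocol and SAP*

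**What the plan says.** Section 6.3.1 plans the second randomization so that eligible ertugliflozin participants "will be randomized in a 1:1 ratio to either stay on ertugliflozin 5 mg or up-titrate to ertugliflozin 15 mg". Section 8.1.14 then gives the unblinded statistician who supports the DMC a way to depart from that: the ratio "may be adjusted in order to achieve approximately 30 participants in the ertugliflozin 15 mg arm".

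The analysis of H2 and H3 is a weighted ANCOVA. Placebo participants and ertugliflozin participants who were not re-randomized get weight 1. For H2, "All participants on ertugliflozin who were re-randomized to 15 mg at Visit 5/Week 12 have a weight of 2", and those re-randomized to 5 mg get 0. For H3 the roles swap: "Participants who were re-randomized to 5 mg at Visit 5/Week 12 have a weight of 2", and those on 15 mg get 0. Section 9.1 repeats the rule ("Participants who were re-randomized to 15 mg at Visit 5/Week 12 have a weight of 2"). Neither section makes the weights depend on the ratio used, and Section 9 mentions no ratio other than 1:1.

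Section 9.6 defines the strategy that H2 is meant to estimate: "Dose-optimized ertugliflozin consists of participants who were randomized to ertugliflozin and either did not meet the re-randomization criterion at Week 12", or met it and were assigned 15 mg.

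**The concern.** The weight of 2 lets the re-randomized participants who stay in the analysis stand in for everyone who was eligible. The ertugliflozin mean then keeps its true mix of eligible and other participants. That mix belongs to the strategy and does not depend on the allocation ratio. With any allocation probability other than 1/2, a weight of 2 gives the eligible group too much or too little influence.

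This matters because eligibility selects on outcome: a fingerstick A1C of at least 7.0% at Week 12. The model adjusts for baseline A1C, age and insulin stratum. It has no term for Week 12 A1C or re-randomization status, and placebo is unweighted, so nothing absorbs a wrong mix. H2 is also the gate to H3.

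Timing adds to the concern. Section 9.9 records that "all randomized participants have either completed on or off study medication or have discontinued from the study in Phase A", so the ratio history is already fixed. For changes made before unblinding, Section 9 says that if "changes are made to primary and/or key secondary hypotheses, or the statistical methods related to those hypotheses, then the protocol will be amended". After unblinding, a correction would be post hoc.

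**Working it through.** **Reproducing the plan's figures.** At 1:1 the weight is 1/0.5 = 2. The 13% relative power loss in Section 9.9 also fits 1:1. Take 110 and 55 participants, effect -0.6, SD 1.5:

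- Unweighted: SE = 1.5 × √(1/110 + 1/55) = 0.248, power 67.8%.
- 60 re-randomized at 1:1 (30 at weight 2, 50 at weight 1): model-based SE = √[2.25 × (165/135) × (1/110 + 1/55)] = 0.274, power 59.1%.
- Relative loss: 1 - 59.1/67.8 = 12.8%.

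**Share of the eligible group.** With E eligible of 110, and n15 and n5 assigned to each dose:

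- true share = E/110
- H2 share = 2·n15/(110 - E + 2·n15)
- H3 share = 2·n5/(110 - E + 2·n5)

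E is not given in the documents, so it is assumed. Each case reaches 30 on 15 mg; ratios are 15 mg to 5 mg.

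| Case | True share | H2 share | H3 share | Correct weights (H2, H3) |
|---|---|---|---|---|
| (a) E = 45, 2:1 | 45/110 = 0.409 | 60/125 = 0.480 | 30/95 = 0.316 | 1.50, 3.00 |
| E = 60, 1:1 | 60/110 = 0.545 | 60/110 = 0.545 | 60/110 = 0.545 | 2.00, 2.00 |
| (b) E = 75, 2:3 | 75/110 = 0.682 | 60/95 = 0.632 | 90/125 = 0.720 | 2.50, 1.67 |

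**Size of the gap.** The gap is the baseline-adjusted Week 24 difference, eligible minus not eligible. Section 9.9's planning covariance gives a Week 12 variance of 1.17 and a Week 12–24 covariance of 0.8, so the slope is 0.8/1.17 = 0.684. If baseline A1C is nearly constant and the upper 40.9% are eligible, the Week 12 means differ by √1.17 × 0.3885/(0.409 × 0.591) = 1.74, giving a gap of 0.684 × 1.74 = 1.19. An assumed baseline SD of 0.9 with slope 0.8 gives 0.99. Halving the Week 12–24 slope gives 0.49. The range used is 0.5 to 1.2.

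**Bias = (weighted share - true share) × gap.**

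| Case | H2, gap 0.5 to 1.2 | H3, gap 0.5 to 1.2 |
|---|---|---|
| (a) | +0.035 to +0.085 | -0.047 to -0.112 |
| (b) | -0.025 to -0.060 | +0.019 to +0.046 |

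With fixed weights only the final counts matter, so a ratio changed halfway that still reaches 30 gives the same bias as (a). A halfway change to 2:1 that stops near 26 gives about 0.04 each way.

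**Simulation.** 20,000 trials per case, weighted ANCOVA on baseline, planning covariance, no missing data. The H1 gate uses the stated 0.134 mixture prior and an equal-tailed 95% interval. H2 and H3 are tested at one-sided 2.5%, taking alpha = 0.05 as two-sided.

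- (a), no drug effect, gap 0.99: fixed weights give bias +0.067 (H2) and -0.098 (H3); correct weights give -0.002 and -0.008. H3 error with fixed weights is 6.1% before gating and 0.75% after.
- (b), no drug effect: fixed weights give -0.053 (H2) and +0.037 (H3). H2 error is 3.9% before gating and 2.3% after.
- (a), effect -0.6: P(H1 and H2 succeed) is 50.5% with fixed and 62.1% with correct weights. At gap 0.5 it is 56% against 63%.
- (a), gap 1.0, 5 mg inert, 15 mg lowering A1C by 1.0 in the re-randomized: H3 is falsely declared in 5.4% with fixed weights, against 3.0% with correct weights and 2.5% at 1:1.

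**The case against.** The strongest objection is that the problem is conditional. The ratio may be adjusted; no document says it was. Every stated ratio is 1:1 or about half, and the 13% power loss is recovered with 60 re-randomized at 1:1. At 1:1 the weights are exactly right, and a chance imbalance under true 1:1 is not bias. This stands, and cases (a) and (b) are illustrations. If the 15 mg arm was dropped, H2 and H3 are not tested and the point falls away.

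The gap may also be smaller than the upper figures. The value 1.2 needs a nearly constant baseline, although entry A1C runs up to 10.0%. The planning covariance is listed under the TE estimand, whereas H2 and H3 use TP, which keeps post-rescue data. The weight-1 group includes insulin users who missed only the glucose criterion and participants who stopped medication before Week 12. Fingerstick error dilutes selection too: an assumed 0.5 points of noise lowers 0.99 to 0.92. These points narrow the bias without removing it.

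On error rates, gating removes the excess under a global null in these simulations. However, the simulated H1 gate passes 4.7% under the null against the SAP's stated 10%, so the gated null rates could be higher under the SAP's own gate, though never above the ungated ones. The false-H3 scenario needs an inert 5 mg dose, against the plan's assumption of equal efficacy. In (a), the H2 bias works against the drug, and the chance of winning all three hypotheses hardly moves (47.9% fixed, 48.8% correct, in 6,000 trials), because H3 gains what H2 loses. That offset does not make either estimate right.

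**Conclusion.** The concern holds. The protocol permits a ratio change that the prespecified estimator cannot handle, and following both sections as written would then generally bias H2 and H3 in opposite directions. In the cases examined the bias is at most about 0.11 points, or 0.4 of a standard error near 0.27 (0.112/0.27), and it is zero if the ratio stayed 1:1.

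The practical consequences in case (a) at gap 1.0 are a loss of about 12 percentage points in the chance of passing H1 and H2 (62.1 - 50.5), and a false-H3 rate of 5.4% instead of 3.0% if only 15 mg works. These rest on the assumed number eligible, the assumed gap, no missing data and the simulated H1 gate. This should be fixed before unblinding, but it does not touch the primary analysis.

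**What to change.** Amend Sections 9.1 and 9.6.1 before unblinding:

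- **H2 weight** = 1/(probability of assignment to 15 mg in force for that participant's second-randomization date and insulin stratum); 0 if assigned 5 mg.
- **H3 weight** = 1/(probability of assignment to 5 mg in force); 0 if assigned 15 mg.
- Weight 1 stays for placebo and for ertugliflozin participants not re-randomized.
- Use the probability in force, not realized counts, so that chance imbalance at 1:1 leaves the weight at 2.
- Report the second-randomization ratio history in the CSR.
- Show a robust-variance result beside the model-based one.

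The cost is one amendment to Section 9. The blinded team can write the rule without seeing the ratio history, and if the ratio never moved the H2 and H3 estimates and model-based tests do not change. If it moved, the weights become more variable. In (a) the SD of the H3 estimate rises from 0.272 to 0.283, or from 0.269 to 0.294 for a late change to 5:1. The model-based SE is then slightly too small (H3 one-sided error of 3.3–4.0% before gating, against 2.7% at 1:1), which is why the robust result is needed.

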The RD analysis may not be feasible due to insufficient observed Week 24 data post discontinuation of study medication. If the number of RD participants per group is at least 50% of participants who discontinue from study medication per arm, then RD will be the primary approach to impute missing data for the TP estimand. If at least one group has either less than 50% RD participants or fewer than 5 total RD participants, then RD will not be performed, and WI will become the primary analysis method. If the minimum data requirement for the RD method is met, then WI will be implemented as a sensitivity approach for the TP estimand. The WI analysis assumes participants who prematurely discontinued from the study or who have an intermittent missing Week 24 value would have a 'washout' of any potential effect of the assigned study medication.

For all analyses involving simulated data, a seed of 8835059 will be used for random number generation.

A constrained longitudinal data analysis (cLDA) model, based on Liang and Zeger [Liang, K.-Y. and Zeger, S. L. 2000], will be used for analyses addressing the TE estimand for A1C mean change from baseline and FPG mean change from baseline. Time will be treated as a categorical variable so that no restriction is imposed on the trajectory of the means over time. The cLDA model will also adjust for treatment, the age stratum, the insulin use stratum, and the interaction of time by treatment. The cLDA model assumes a common mean across treatment groups at baseline within each age and insulin use category (due to randomization) but different means between categories, and a different mean for each treatment at each of the post-baseline timepoints. In the cLDA model, the response vector consists of baseline and the values observed at each post-baseline timepoint. The treatment difference in terms of mean change from baseline to a given timepoint will be estimated and tested from this model. An unstructured covariance matrix will be used to model the correlation among repeated measurements.

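### In the retrieved-dropout imputation for H2 and H3, the imputation mean and SD are fixed across all 100 datasets, so Rubin's rule leaves out the uncertainty of a mean that may rest on five participants; the effect is modest and arises only if that branch is run.

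*Combined protocol and SAP*

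**What the plan says.** Section 9.6.1 sets out the RD steps for H2 and H3, "using Rubin's rule for 100 total imputed datasets". In step 1a the imputation distribution is normal: "the expected change from baseline value is set to the estimated mean change from baseline value from the RD participants" of the same arm. Its spread is also an estimate from the data: "The standard deviation will be the RMSE derived from the ANCOVA model described above and estimated based on all participants with Week 24 data". Step 1b adds that "each of the 100 resulting datasets will contain the original non-missing data" together with the imputed values. The weighted ANCOVA estimates are then combined by Rubin's rule, "which accounts for between and within imputation variability".

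RD is the first-choice missing-data method for both key secondary hypotheses (Table 7). It gives way to washout imputation (WI) if any group has "either less than 50% RD participants or fewer than 5 total RD participants". The 50% is counted against participants who stopped study medication. If RD is used, WI becomes a sensitivity analysis.

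**The concern.** Rubin's rule gives a valid variance when each dataset is imputed from parameters that are themselves drawn, so that the spread between datasets includes the uncertainty about those parameters. Here the observed data are the same in every dataset and no step draws or resamples anything before the missing values are generated. The RD mean and the RMSE are therefore constants across the 100 datasets, and the between-imputation variance contains residual noise only.

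The fixed SD matters little, because it is estimated from everyone with Week 24 data. The fixed mean matters more, because it may rest on five people. H2 and H3 are formal tests at alpha 0.05 (Section 9.8). Intervals that are too narrow would raise their error rate above nominal, from a source that the plan does not mention.

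**Working it through.** **The plan's own figure.** No figure is given for RD interval width or RD type I error. The only number for H2/H3 is power: Section 9.9 takes 13% off the primary power, 0.80 × (1 − 0.13) = 0.696, which reproduces its 70%. Section 9.1 says 74%, a separate discrepancy to reconcile. Section 9.9 also says the error and power work used WI, so neither figure describes RD.

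**Inputs.** 110 ertugliflozin and 55 placebo; SD 1.5%; 3.9% discontinuation from study medication (Section 9.9). At least 156 of 165 with complete Week 24 data (Section 4.1), so about 9 missing. At least 5 RD participants per group (Section 9.6.1). Assumed: alpha 0.05 is two-sided (the plan does not say), a common SD, and RD and missing participants spread at random over the weights.

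**Closed form, no weights.** Take an arm with n participants, r RD and m missing.
- Actual variance: each RD value carries weight 1 + m/r, so [(n − m − r) + r(1 + m/r)²]σ²/n² = (n + m + m²/r)σ²/n². Using 100 imputations adds 0.01m.
- Variance reported as written: (n + 1.01m)σ²/n².
- Omitted: (m²/r)σ²/n².

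Example with 5 RD and 5 missing in each arm:
- As written: 115.05/110² + 60.05/55² = 0.02936, SE = 1.5 × √0.02936 = 0.2570.
- Correct: 120.05/110² + 65.05/55² = 0.03143, SE = 0.2659.
- Ratio 0.967; type I error 2 × [1 − Φ(1.96 × 0.967)] = 0.058.

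| Ertugliflozin RD/missing | Placebo RD/missing | SE as written ÷ correct SE | Type I error |
|---|---|---|---|
| 5/6 | 5/3 (9 missing in all) | 0.980 | 0.055 |
| 5/5 | 5/5 | 0.967 | 0.058 |
| 10/10 | 5/5 | 0.961 | 0.060 |
| 16/16 | 8/8 | 0.942 | 0.065 |
| 5/15 | 5/8 | 0.893 | 0.080 |

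The last row has 23 of 165 missing (14%). Under the 50% rule at least 10 of the 15 and 3 of the 8 must be intermittent rather than discontinuers. Unweighted simulation of the written steps (100 imputations) gave type I error of 0.054, 0.057, 0.061 and 0.082 for the last four rows.

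**With the H2 weights** (15,000 simulated trials per case, Monte Carlo error about 0.2 points). The number re-randomized is not given, so 30 and 36 participants with weight 2 were assumed.

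| Case | SE as written → with draws | Type I error as written → with draws |
|---|---|---|
| 5 RD, 5 missing per group; 30 with weight 2 | 0.288 → 0.300 | 0.055 → 0.047 |
| 5 RD, 5 missing per group; 36 with weight 2 | 0.296 → 0.309 | 0.055 → 0.045 |
| 5 RD per group, 10 and 8 missing; 36 with weight 2 | 0.305 → 0.338 | 0.063 → 0.041 |

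Shorter runs of 6,000 trials ranged from 0.049 to 0.058 in the first two cases. The weighted model SE is itself 1-4% too wide with complete data, which offsets part of the shortfall.

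**How likely is the RD branch?** 3.9% of 165 is 6.4 discontinuers, about 4.3 on ertugliflozin and 2.1 on placebo. RD needs at least 5 + 5 = 10 of them retrieved, which is 6.1% of 165. At 3.9% the binomial chance of even five placebo discontinuers is about 6%, and of five or more in both groups about 3%.

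**The case against.** The strongest reply is that this code will probably never run. The planned discontinuation rate does not support five retrieved dropouts per group. Section 9.9 says power was based on WI because all participants had already finished or left Phase A, which suggests the sponsor expects WI. Even if RD runs, WI follows as a sensitivity analysis, H2 is tested only after H1 succeeds, and Section 9.8 already accepts a study-wise error above 0.05. All of this stands and limits the weight of the point. It does not make the written steps correct, and RD is still the named first choice.

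Stronger readings are tempting but not supported:
- A reader might infer that most of the between-imputation variance is lost. The omitted term m²/r at most equals the included term m while m ≤ r, which the 50% rule secures for discontinuers. It is larger only if intermittent missing values push m above r.
- A reader might take a 4% shortfall in the SE as the worst case. That is the size at or near 5 RD and 5 missing per group; other allowed cases reach 6% or, with many intermittent gaps, about 11%.
- A reader might extend the criticism to WI, which also plugs in estimated parameters. There, missing ertugliflozin values come from the placebo model, so the arm means are positively correlated and Rubin's variance tends to be too large. A 5,000-trial simulation with 4/2 and 6/3 missing, assuming Rubin's rule is used for WI too, gave SE ratios of 1.04-1.07 and type I error of 3.7-4.1%. Undercoverage is not the problem on that branch.
- A reader might extend it to H1. Those RD steps are in a figure not available here, so nothing is claimed.

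**Conclusion.** The point holds for the RD steps of H2 and H3: the imputation is improper as written, and the statement about what Rubin's rule accounts for is only partly met. If the branch runs, the unweighted SE is about 2-6% too small and two-sided type I error about 5.5-6.5%. For the roughly 9 missing values the protocol expects, the figures are 2% and 5.5%. Larger shortfalls need many intermittent missing values. Under the H2 weights the error is about 5-6% near the minimum RD counts, and 6.3% in the heavier case shown.

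This is a modest and conditional defect in a confirmatory analysis, worth correcting because the correction is nearly free. It rests on the assumptions listed with the calculation, and on the five-participant minimum being counted in the same group from which the mean is taken. The plan does not say whether the minimum applies to the pooled ertugliflozin group or to the smaller H2 and H3 groups. If it is pooled, the H2/H3 mean could rest on fewer than five.

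**What to change.** Amend step 1a so that, in each of the 100 datasets, σ² is first drawn from its scaled inverse chi-square posterior (ANCOVA residual sum of squares and degrees of freedom). Next, each group's RD mean is drawn from N(observed RD mean, σ²/r), where r is that group's number of retrieved dropouts. Only then are the missing values drawn. Resampling participants and re-estimating both quantities within each imputation would serve as well. State also in which group the minimum of five is counted. Leave the WI steps as they are on this account.

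The cost is one SAP sentence and a few lines of code before unblinding. Intervals widen by about 4% at 5 RD and 5 missing per group, and the weighted test becomes mildly conservative (about 4.5-4.7% there, 4.1% in the heavier case). Simulated H2 power at −0.6% falls from about 52% to 49% in the boundary case with 36 participants at weight 2.
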